3.3.5 Rationale for Patient-Reported Outcome Assessments

PRO assessments improve our understanding of a treatment's impact from the patient's perspective, an important consideration in many of today's quality initiatives (91). This study will therefore employ the EORTC QLQ-LC13 instrument to assess self-reported outcomes in all enrolled patients (Appendix 4). The EORTC QLQ-LC13 is a lung-cancer-specific module designed to supplement the more general EORTC QLQ-C30 core measure (92). Developed for use with lung cancer patients undergoing anticancer therapy, the EORTC QLQ-LC13 includes 13 items that address key lung cancer symptoms (cough, hemoptysis, dyspnea, and site-specific pain), treatment-related adverse effects (sore mouth, dysphagia, peripheral neuropathy and alopecia) and pain medication. The dysphagia scale is multi-item, while the rest are single-item scales.

In addition, patients in this trial will complete the EuroQol EQ-5. The EQ-5D-5L is a self-report health status questionnaire that consists of six questions used to calculate a health utility score for use in health economic analysis (93-96). The EuroQol EQ-5D has two components: a five-item health state profile that assesses mobility, self-care, usual activities, pain/discomfort and anxiety/depression, as well as a visual analog scale that measures health state. Published weighting systems allow for creation of a single summary score. Overall scores range from 0 to 1, with low scores representing a higher level of dysfunction. The EQ-5D will be utilized in this study for economic modeling.

3.3.6 Rationale for Allowing Patients to Continue Atezolizumab Treatment Beyond Initial Progression

Anti-tumor immune responses such as those associated with atezolizumab may result in objective responses that are delayed and that can be preceded by initial apparent radiological progression. This initial apparent progression may occur as a result of either delayed anti-tumor activity and/or robust tumor immune cell infiltration with a concomitant increase in tumor size (pseudo-progression). In addition, lesions that might otherwise be undetectable with conventional imaging may increase in size as a result of these processes and be recorded as new lesions (97).

Furthermore, prior clinical evidence indicates that treatment with atezolizumab beyond apparent PD can have beneficial effects in patients with NSCLC:

- In Study PCD4989g, several patients with NSCLC who progressed by RECIST v1.1 criteria continued on atezolizumab treatment and demonstrated durable anti-tumor activity. In some responding patients, the growth of known lesions or the appearance of new radiographic lesions were shown to contain immune cells and no viable cancer cells on biopsy.
- In POPLAR, 47% of patients who continued atezolizumab after PD had subsequent stable or reduced target lesions relative to baseline (80). Moreover, in the atezolizumab arm of the study, OS from the time of first RECIST v1.1 PD was 11.1 months for patients who continued atezolizumab post PD versus 8.3 months for patients who received a different anti-cancer therapy post PD. These data suggest that continuation of atezolizumab after progression can, in some patients, have a positive benefit-risk profile.

Based on the previous considerations, this study will allow patients to remain on atezolizumab after apparent radiographic progression, provided the benefit-risk ratio is judged to be favorable by the investigator. Patients should be discontinued for unacceptable toxicity or symptomatic deterioration attributed to disease progression as determined by the investigator after an integrated assessment of radiographic data and clinical status, as described in Section 4.6.2.

4. **MATERIALS AND METHODS**

4.1 **PATIENTS**

This study will enroll approximately 600 patients with Stage IIIb or Stage IV NSCLC who have progressed following standard systemic chemotherapy (including if given in combination with anti-PD-1 therapy or after anti-PD-1 as monotherapy). Patients with a previously detected sensitizing EGFR mutation or ALK fusion oncogene must have received targeted therapy followed by one line of standard systemic chemotherapy prior to receiving atezolizumab. Overall, patients should not have received more than two lines of systemic chemotherapy. Patients will also be eligible if they discontinued first-line or second-line therapy due to intolerance.

4.1.1 **Inclusion Criteria**

Patients must meet the following criteria for study entry:

1. Signed Informed Consent Form
1. Age \geq 18 years
2. Able to comply with the study protocol, in the investigator's judgment
3. Histologically or cytologically documented Stage IIIb or Stage IV NSCLC that has progressed following standard systemic chemotherapy (including if given in combination with anti-PD-1 therapy, after anti-PD-1 as monotherapy, or after TKI therapy). Patients with a previously detected sensitizing EGFR mutation or ALK

fusion oncogene must have received targeted therapy (TKI), followed by at least one line of standard systemic chemotherapy, prior to receiving atezolizumab. Overall, patients should not have received more than two lines of standard systemic chemotherapy. Patients who have discontinued first-line or second-line therapy due to intolerance are also eligible

- Staging must be according to the UICC/AJCC system, 7th edition (Detterbeck et al. 2009) (see [Appendix 8](#))
- Pathological characterization may be conducted on tumor specimens from earlier stage disease, but the tumor samples must be sufficient to distinguish squamous or non-squamous histology
- Chemotherapy regimens will be counted based on interval disease progression, and not on the number of agents or the number of switches in agents (e.g., a first-line or second-line therapy that consists of several cycles of a platinum doublet and subsequent maintenance therapy that introduces or switches to a new chemotherapy agent without interval disease progression will all be considered one chemotherapy regimen)
- Patients with a previously-detected sensitizing EGFR mutation must have experienced disease progression (during or after treatment) on an EGFR TKI (erlotinib, gefitinib, osimertinib, etc.)
- Patients with a previously detected ALK fusion oncogene must have experienced disease progression (during or after treatment) with crizotinib, alectinib, or another ALK inhibitor
- Prior radiation therapy is allowed, provided that the patient has recovered from any toxic effects thereof. Combined radiation/chemotherapy treatment constitutes a single regimen
- Combined radiation/chemotherapy treatment (chemoradiation) counts as one prior chemotherapy regimen if < 6 months have elapsed between the last dose and the date of recurrence
- Adjuvant/neoadjuvant chemotherapy is not counted as a line of treatment
- Debulking surgery and anticancer agents used for pleurodesis are not counted as lines of therapy

4. The last dose of prior systemic anticancer therapy or targeted therapy must have been administered \geq 21 days prior to study treatment initiation
5. The last dose of prior anti-PD-1 therapy must have been administered
 - Nivolumab must have been discontinued \geq 14 days and pembrolizumab \geq 21 days prior to study treatment initiation, providing that these treatments were not administered in a clinical trial setting
6. Measurable disease, as defined by Response Evaluation Criteria for Solid Tumors, Version 1.1 (RECIST v1.1)

7. Patients with asymptomatic CNS metastases (treated or untreated), as determined by CT or MRI evaluation during screening and prior radiographic evaluation, are eligible
8. ECOG performance status 0, 1, or 2 [[Appendix 7](#)]
9. Life expectancy \geq 12 weeks
10. Adequate hematologic and end-organ function, defined by the following laboratory results obtained within 2 weeks prior to the first study treatment:
 - Absolute neutrophil count \geq 1500 cells/ μ L (without granulocyte colony-stimulating factor support within 2 weeks prior to the first study treatment)
 - White blood cell count $>$ 2500/ μ L
 - Lymphocyte count \geq 500/ μ L
 - Platelet count \geq 100,000/ μ L (without transfusion within 2 weeks prior to the first study treatment)
 - Hemoglobin \geq 9.0 g/dL (patients may be transfused or receive erythropoietic treatment to meet this criterion)
 - Aspartate transaminase (AST), alanine transaminase (ALT), and alkaline phosphatase \leq 2.5 times the upper limit of normal (ULN), with the following exceptions:
 - Patients with documented liver metastases: AST and/or ALT \leq 5 \times ULN
 - Patients with documented liver or bone metastases: alkaline phosphatase \leq 5 \times ULN
 - Serum bilirubin \leq 1.5 \times ULN. Patients with known Gilbert's Syndrome who have serum bilirubin level \leq 3 \times ULN may be enrolled.
 - Calculated creatinine clearance \geq 15 mL/min (Cockcroft-Gault formula)
 - International normalized ratio (INR) and activated partial thromboplastin time (aPTT) \leq 1.5 \times ULN. This applies only to patients who are not receiving therapeutic anticoagulation agents
 - Patients receiving therapeutic anticoagulation agents must be on a stable dose
 - HIV-positive patients are allowed, so long as they are on stable anti-retroviral therapy, have a CD4 count \geq 200 cells/ μ L, and have an undetectable viral load at the time of screening
11. For women of childbearing potential: agreement to remain abstinent (refrain from heterosexual intercourse) or use contraceptive methods that result in a failure rate of $<$ 1% per year during the treatment period and for at least 5 months after the last dose of atezolizumab
 - A woman is considered to be of childbearing potential if she is postmenarchal, has not reached a postmenopausal state (\geq 12 continuous months of amenorrhea with no identified cause other than menopause), and has not undergone surgical sterilization (removal of ovaries and/or uterus)

- Examples of contraceptive methods with a failure rate of < 1% per year include bilateral tubal ligation, male sterilization, established, proper use of hormonal contraceptives that inhibit ovulation, hormone-releasing intrauterine devices, and copper intrauterine devices
- The reliability of sexual abstinence should be evaluated in relation to the duration of the clinical trial and the preferred and usual lifestyle of the patient. Periodic abstinence (e.g., calendar, ovulation, symptothermal, or postovulation methods) and withdrawal are not acceptable methods of contraception

12. Patients must have recovered (i.e., improvement to Grade 1 or better) from all acute toxicities from previous therapy, excluding alopecia and toxicities related to prior anti-PD-1-therapy

4.1.2 Exclusion Criteria

Patients who meet any of the following criteria will be excluded from study entry:

1. Symptomatic CNS metastases
13. Spinal cord compression not definitively treated with surgery and/or radiation or previously diagnosed and treated spinal cord compression without evidence that disease has been clinically stable for \geq 2 weeks prior to study treatment initiation
14. Leptomeningeal disease
15. Uncontrolled pericardial effusion or ascites requiring recurrent drainage procedures
16. Pregnant or lactating, or intending to become pregnant during the study
 - Women who are not postmenopausal (postmenopausal defined as \geq 12 months of non-drug-induced amenorrhea) or surgically sterile must have a negative serum pregnancy test result within 2 weeks prior to initiation of study drug
17. Evidence of significant uncontrolled concomitant disease that could affect compliance with the protocol, including significant liver disease (such as cirrhosis, uncontrolled major seizure disorder, or superior vena cava syndrome)
18. Significant cardiovascular disease, such as New York Heart Association cardiac disease \geq Class III, myocardial infarction within 3 months, unstable arrhythmias, or unstable angina
 - Patients with known coronary artery disease or left ventricular ejection fraction < 50% must be on a stable medical regimen that is optimized in the opinion of the treating physician, in consultation with a cardiologist if appropriate
19. Significant renal disorder requiring dialysis or indication for renal transplant
20. Treatment with any other investigational agent or participation in another clinical trial with therapeutic intent within 28 days prior to study treatment initiation
21. Major surgical procedure within 4 weeks prior to study treatment initiation or anticipation of need for a major surgical procedure during the course of the study other than for diagnosis

22. Inability to understand the local language(s) for which the EORTC QLQ-LC13 and EuroQol EQ-5D-5L questionnaires are available (see [Appendix 4](#) for English versions)
23. History of severe allergic, anaphylactic, or other hypersensitivity reactions to chimeric or humanized antibodies or fusion proteins
24. Known hypersensitivity or allergy to biopharmaceuticals produced in Chinese hamster ovary cells or any component of the atezolizumab formulation
25. History of autoimmune disease ([Appendix 5](#)) are allowed if controlled and on stable treatment (i.e., same treatment, same dose) for the last 12 weeks, with the exception of:
 - Patients taking concurrent abatacept or belatacept treatment, unless therapy has been withdrawn for > 8 weeks
 - Patients with a history of serious or life threatening immune-related events
 - No more than 1 concomitant autoimmune disease at the time of study entry is allowed unless one of them is:
 - Autoimmune-mediated hypothyroidism on a stable dose of thyroid replacement hormone
 - Controlled Type I diabetes mellitus on a stable dose of insulin regimen
 - A medical history of such entities as atopic disease or childhood arthralgias, where the clinical suspicion of autoimmune disease is low. In addition, transient autoimmune manifestations of an acute infectious disease that resolved upon treatment of the infectious agent are not excluded (e.g., acute Lyme arthritis)
26. Prior allogeneic stem cell or solid organ transplantation
27. History of idiopathic pulmonary fibrosis, including pneumonitis, drug-induced pneumonitis, organizing pneumonia (i.e., bronchiolitis obliterans, cryptogenic organizing pneumonia), or evidence of active pneumonitis on screening chest computed tomography (CT) scan
 - History of radiation pneumonitis in the radiation field (fibrosis) is permitted
28. Active tuberculosis
 - In patients who have a potentially high likelihood of latent tuberculosis (e.g., recent contact with an infectious carrier, residence in a locale with high TB burden), absence of *Mycobacterium tuberculosis* infection must be confirmed before enrollment according to local practice standards
29. Administration of a live, attenuated vaccine within 4 weeks prior to study treatment initiation
 - Influenza vaccination should be given during influenza season only (e.g., approximately October to March in the Northern Hemisphere).

- Patients must not receive live, attenuated influenza vaccine (e.g., FluMist®) within 4 weeks prior to study treatment initiation or at any time during the study
- 30. Prior treatment with CD137 agonists or immune checkpoint blockade therapies other than anti-PD-1 therapy, including anti-PD-L1 therapeutic antibodies
- 31. Treatment with systemic immunostimulatory agents (including, but not limited to, interferons or interleukin-2) within 4 weeks or five half-lives of the drug, whichever is longer, prior to initiation of study treatment
- Prior cancer vaccines and cellular immunotherapy are permitted
- 32. Specifically for patients without autoimmune disease: treatment with systemic corticosteroids or other systemic immunosuppressive medications (including but not limited to prednisone, dexamethasone, cyclophosphamide, azathioprine, methotrexate, thalidomide, and anti-tumor necrosis factor [TNF] agents) within 2 weeks prior to study treatment initiation, or anticipated requirement for systemic immunosuppressive medications during the trial
 - For patients with CNS metastases, use of prednisone at a stable dose (or dose equivalent) of \leq 20 mg/day is acceptable
 - The use of inhaled corticosteroids for chronic obstructive pulmonary disease, mineralocorticoids (e.g., fludrocortisone) for patients with orthostatic hypotension, and low-dose supplemental corticosteroids for adrenocortical insufficiency and topical steroids for cutaneous diseases are allowed

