 - Patients with documented liver metastases: AST and/or ALT $\leq 5 \times$ ULN
 - Patients with documented liver or bone metastases: alkaline phosphatase $\leq 5 \times$ ULN
- Serum bilirubin $\leq 1.5 \times$ ULN. Patients with known Gilbert's Syndrome who have serum bilirubin level $\leq 3 \times$ ULN may be enrolled.
- Calculated creatinine clearance ≥ 15 mL/min (Cockcroft-Gault formula)
- International normalized ratio (INR) and activated partial thromboplastin time (aPTT) $\leq 1.5 \times$ ULN. This applies only to patients who are not receiving therapeutic anticoagulation agents
- Patients receiving therapeutic anticoagulation agents must be on a stable dose
- HIV-positive patients are allowed, so long as they are on stable anti-retroviral therapy, have a CD4 count ≥ 200 cells/ μ L, and have an undetectable viral load at the time of screening

12. For women of childbearing potential: agreement to remain abstinent (refrain from heterosexual intercourse) or use contraceptive methods that result in a failure rate of $< 1\%$ per year during the treatment period and for at least 5 months after the last dose of atezolizumab

- A woman is considered to be of childbearing potential if she is postmenarchal, has not reached a postmenopausal state (≥ 12 continuous months of amenorrhea with no identified cause other than menopause), and has not undergone surgical sterilization (removal of ovaries and/or uterus)
- Examples of contraceptive methods with a failure rate of $< 1\%$ per year include bilateral tubal ligation, male sterilization, established, proper use of hormonal contraceptives that inhibit ovulation, hormone-releasing intrauterine devices, and copper intrauterine devices
- The reliability of sexual abstinence should be evaluated in relation to the duration of the clinical trial and the preferred and usual lifestyle of the patient. Periodic abstinence (e.g., calendar, ovulation, symptothermal, or postovulation methods) and withdrawal are not acceptable methods of contraception

13. Patients must have recovered (i.e., improvement to Grade 1 or better) from all acute toxicities from previous therapy, excluding alopecia and toxicities related to prior anti-PD-1-therapy

Exclusion Criteria

Patients who meet any of the following criteria will be excluded from study entry:

1. Symptomatic CNS metastases

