- Controlled Type I diabetes mellitus on a stable dose of insulin regimen
- A medical history of such entities as atopic disease or childhood arthralgias where the clinical suspicion of autoimmune disease is low. In addition, transient autoimmune manifestations of an acute infectious disease that resolved upon treatment of the infectious agent are not excluded (e.g., acute Lyme arthritis).

Caution should be used when considering atezolizumab for patients who have previously experienced a severe or life-threatening skin adverse reaction while receiving another immunostimulatory anti-cancer agent. Please contact the Medical Monitor regarding any uncertainty over autoimmune exclusions.

Acute disseminated encephalomyelitis	Epidermolysis bullosa acquista	Ord's thyroiditis
Addison's disease	Gestational pemphigoid	Pemphigus
ANCA positive vasculitis	Giant cell arteritis	Pernicious anemia
Ankylosing spondylitis	Glomerulonephritis	Polyarteritis nodosa
Antiphospholipid antibody syndrome	Goodpasture's syndrome	Polyarthritis
Aplastic anemia	Graves' disease	Polychondritis
Autoimmune hemolytic anemia	Guillain-Barré syndrome	Polyglandular autoimmune syndrome
Autoimmune hepatitis	Hashimoto's disease	Polymyositis
Autoimmune hypoparathyroidism	IgA nephropathy	Primary biliary cirrhosis
Autoimmune hypophysitis	Inflammatory bowel disease	Psoriasis
Autoimmune myocarditis	Interstitial cystitis	Pyoderma gangrenosum
Autoimmune oophoritis	Kawasaki's disease	Reactive arthritis
Autoimmune orchitis	Lambert-Eaton myasthenia syndrome	Rheumatoid arthritis

Appendix 5

Preexisting Autoimmune (Chronic Inflammatory) Diseases (cont'd)

Autoimmune thrombocytopenic purpura	Lupus erythematosus	Sarcoidosis
Behcet's disease	Lyme disease – chronic	Scleroderma
Bullous pemphigoid	Mixed connective tissue disease	Sjögren's syndrome
Celiac disease	Mooren's ulcer	Stiff-Person syndrome
Chronic fatigue syndrome	Morphea	Takayasu's arteritis
Chronic inflammatory demyelinating polyneuropathy	Multiple sclerosis	Ulcerative colitis
Chung-Strauss syndrome	Myasthenia gravis	Vitiligo
Crohn's disease	Neuromyotonia	Vogt-Kovanagi-Harada disease
Dermatomyositis	Opsoclonus myoclonus syndrome	Wegener's granulomatosis
Dysautonomia	Optic neuritis	

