Although most immune-related adverse events observed with immunomodulatory agents have been mild and self-limiting, such events should be recognized early and treated promptly to avoid potential major complications. Discontinuation of atezolizumab may not have an immediate therapeutic effect, and in severe cases, immune-related toxicities may require acute management with topical corticosteroids, systemic corticosteroids, or other immunosuppressive agents.

The investigator should consider the benefit–risk balance a given patient may be experiencing prior to further administration of atezolizumab. In patients who have met the criteria for permanent discontinuation, resumption of atezolizumab may be considered if the patient is deriving benefit and has fully recovered from the event. Patients can be re-challenged with atezolizumab only after approval has been documented by both the investigator (or an appropriate delegate) and the Medical Monitor.

DOSE MODIFICATIONS

There will be no dose modifications for atezolizumab in this study.

TREATMENT INTERRUPTION

Atezolizumab treatment may be temporarily suspended in patients experiencing toxicity considered to be related to study treatment. If corticosteroids are initiated for treatment of the toxicity, they must be tapered over ≥ 1 month to the equivalent of ≤ 10 mg/day oral prednisone before atezolizumab can be resumed. If atezolizumab is withheld for > 12 weeks after event onset, the patient will be discontinued from atezolizumab. However, atezolizumab may be withheld for > 12 weeks to allow for patients to taper off corticosteroids prior to resuming treatment. Atezolizumab can be resumed after being withheld for > 12 weeks if the Medical Monitor agrees that the patient is likely to derive clinical benefit. Atezolizumab treatment may be suspended for reasons other than toxicity (e.g., surgical procedures) with Medical Monitor approval. The investigator and the Medical Monitor will determine the acceptable length of treatment interruption.

MANAGEMENT GUIDELINES

PULMONARY EVENTS

Dyspnea, cough, fatigue, hypoxia, pneumonitis, and pulmonary infiltrates have been associated with the administration of atezolizumab. Patients will be assessed for

pulmonary signs and symptoms throughout the study and will have computed tomography (CT) and/or magnetic resonance imaging (MRI) scans of the chest performed at every tumor assessment.

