Diarrhea or colitis, Grade 4	
 • Permanently discontinue atezolizumab and contact Medical Monitor.^c • Refer patient to GI specialist for evaluation and confirmation biopsy. • Initiate treatment with corticosteroids equivalent to 1–2 mg/kg/day IV methylprednisolone and convert to 1–2 mg/kg/day oral prednisone or equivalent upon improvement. • If event does not improve within 48 hours after initiating corticosteroids, consider adding an immunosuppressive agent. • If event resolves to Grade 1 or better, taper corticosteroids over ≥ 1 month.

GI=gastrointestinal.

- ^a Atezolizumab may be withheld for a longer period of time (i.e., > 12 weeks after event onset) to allow for corticosteroids (if initiated) to be reduced to the equivalent of ≤ 10 mg/day oral prednisone. The acceptable length of the extended period of time must be agreed upon by the investigator and the Medical Monitor.
- ^b If corticosteroids have been initiated, they must be tapered over ≥ 1 month to the equivalent of ≤ 10 mg/day oral prednisone before atezolizumab can be resumed.
- ^c Resumption of atezolizumab may be considered in patients who are deriving benefit and have fully recovered from the event. Patients can be re-challenged with atezolizumab only after approval has been documented by both the investigator (or an appropriate delegate) and the Medical Monitor.

ENDOCRINE EVENTS

Thyroid disorders, adrenal insufficiency, diabetes mellitus, and pituitary disorders have been associated with the administration of atezolizumab. Management guidelines for endocrine events are provided in [Table 4](#).

Patients with unexplained symptoms such as headache, fatigue, myalgias, impotence, constipation, or mental status changes should be investigated for the presence of thyroid, pituitary, or adrenal endocrinopathies. The patient should be referred to an endocrinologist if an endocrinopathy is suspected. Thyroid-stimulating hormone (TSH) and free triiodothyronine and thyroxine levels should be measured to determine whether thyroid abnormalities are present. Pituitary hormone levels and function tests (e.g., TSH, growth hormone, luteinizing hormone, follicle-stimulating hormone, testosterone, prolactin, adrenocorticotropic hormone [ACTH] levels, and ACTH stimulation test) and magnetic resonance imaging (MRI) of the brain (with detailed pituitary sections) may help to differentiate primary pituitary insufficiency from primary adrenal insufficiency.

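### The exclusion for serious or life-threatening immune-related events sits inside the autoimmune-disease criterion, so read literally it misses prior anti-PD-1 patients without autoimmune disease, including those whose earlier event Appendix 9 would treat as a reason for permanent discontinuation

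*Protocol*

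**What the plan says.** - **The exclusion.** In Protocol 4.1.2 the autoimmune-disease criterion (printed as no. 25; no. 14 in the synopsis) permits a history of autoimmune disease that is controlled and on stable treatment, then lists exceptions. The second exception is "Patients with a history of serious or life threatening immune-related events". The synopsis and the synopsis copy in SAP Appendix 1 have the same structure. The phrase is nowhere a numbered exclusion of its own.
- **Recovery from earlier toxicity.** Inclusion Criterion 12 in 4.1.1 (no. 13 in the synopsis) requires recovery to Grade 1 or better "from all acute toxicities from previous therapy, excluding alopecia and toxicities related to prior anti-PD-1-therapy". The carve-out has no upper grade limit.
- **Prior anti-PD-1 therapy.** Protocol 1.3 lists these patients among the newly admitted groups. Their own inclusion criterion sets washout times (14 days for nivolumab, 21 for pembrolizumab) and rules out treatment given within a trial. It says nothing about earlier immune toxicity.
- **On-study rule.** Appendix 9 lets a patient who has met the permanent-discontinuation criteria resume only if benefiting and fully recovered. It adds: "Patients can be re-challenged with atezolizumab only after approval has been documented by both the investigator (or an appropriate delegate) and the Medical Monitor".

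**The concern.** A history of a dangerous immune reaction to a drug acting on the same pathway is an obvious thing to screen for when prior anti-PD-1 patients are admitted. The protocol has words for it, but places them where they qualify a different permission. The criterion that does speak to anti-PD-1 toxicity relaxes the recovery requirement.

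Two things are at stake. Two sites could decide differently on the same history. Under the permissive reading, a new patient also gets atezolizumab without a check that the protocol imposes on a patient already under its care.

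**Working it through.** The point turns on the scope of a criterion, so the check is textual. A short calculation then bounds the effect on the primary endpoint.

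**Step 1: scope of the bullet.** It belongs to a list of exceptions to a permission for autoimmune patients. The neighbouring exceptions (abatacept or belatacept use, number of concomitant autoimmune diseases) also concern those patients. The immunosuppression criterion in 4.1.2 is expressly limited to patients without autoimmune disease, so the drafters did separate rules by autoimmune status. Literally, a patient without autoimmune disease is outside the bullet.

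**Step 2: a test patient.** No autoimmune disease; Grade 4 colitis on nivolumab, now resolved; steroids stopped more than 2 weeks ago and none expected; laboratory values within limits.

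| Provision | Does it stop this patient? |
|---|---|
| 4.1.1, recovery to Grade 1 | No: resolved, and anti-PD-1 toxicity is exempt anyway |
| 4.1.1, anti-PD-1 criterion | No: no condition on earlier immune toxicity |
| 4.1.1, laboratory limits | No: met |
| 4.1.2, pneumonitis history | No: lung events only |
| 4.1.2, immunosuppression within 2 weeks, or "anticipated requirement for systemic immunosuppressive medications during the trial" | No: neither applies |
| 4.1.2, "History of severe allergic, anaphylactic, or other hypersensitivity reactions to chimeric or humanized antibodies or fusion proteins" | No: different type of event |
| 4.1.2, cardiovascular or uncontrolled concomitant disease | No: neither present |
| Appendix 5 list | Not by name: inflammatory bowel disease, Crohn's disease and ulcerative colitis are listed, drug-induced colitis is not |
| Appendix 5, severe skin reactions | No: a caution, and for skin only |

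The result is the same for resolved meningoencephalitis (nearest Appendix 5 term: acute disseminated encephalomyelitis) and resolved HLH/MAS (no term).

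**Step 3: the same event on study.** Table 3 requires permanent discontinuation for "Diarrhea or colitis, Grade 4". Table 11 does so for meningoencephalitis of any grade, and Table 14 for suspected HLH or MAS. The Appendix 9 rule on full recovery and two approvals then governs any return to treatment. At entry, the literal text asks for neither.

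**Step 4: where the contrast stops.** The Appendix 9 rule applies only once permanent-discontinuation criteria are met. Other severe events resume without dual approval:
- Grade 3 colitis, once at Grade 1 or better (Table 3).
- Grade 2–4 adrenal insufficiency, once at Grade 1 or better and stable on replacement (Table 4).
- Grade 3 or 4 hyperglycemia, once symptoms resolve and glucose is stable (Table 4).

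**Step 5: effect on the overall primary incidence.** One extra event in 600 patients adds 1/600 = 0.17 percentage points. For a 5% incidence, Protocol Table 12 prints 3.3% to 6.7%, a half-width of (6.7 − 3.3)/2 = 1.7 points. The exact Clopper-Pearson interval for 30/600 is 3.40% to 7.06%, a half-width of 1.83 points. Then 1.83% × 600 = 11.0, so about 11 extra events would match the planned precision. For 60/600 (10%) the exact interval is 7.72% to 12.68%, a half-width of 2.48 points, and 2.48% × 600 = 14.9, so about 15 events. The documents do not say how many patients are exposed to the gap.

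**The case against.** The strongest reply is that the bullet will be read as general. Immune-related events is the protocol's usual term for drug-associated events, which suggests a wider intent than autoimmune disease. Appendix 5 also names autoimmune hepatitis, myocarditis, hypophysitis, myasthenia gravis and Guillain-Barré syndrome. A site matching a prior event to one of these brings the patient into the autoimmune criterion, and the bullet then applies. Appendix 5 further says "Please contact the Medical Monitor regarding any uncertainty over autoimmune exclusions", directly after its caution on earlier immunotherapy skin reactions. All of this stands and narrows the gap. It does not close it: a site that takes the text literally may see no uncertainty to raise, and the three example events have no exact match in the list.

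A second reply is that the Appendix 9 rule governs resumption, not entry. That is correct. It is used here only as the sponsor's own view of when re-exposure needs a documented check.

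A reader might infer that Appendix 9 requires full recovery and dual approval after any severe immune event, and so ask for the same at entry. The documents do not support that, as Step 4 shows. A test built on seriousness would also reach too far: Protocol 5.2.2 counts any event requiring hospitalization as serious, and a full-recovery condition would bar patients stable on hormone or insulin replacement whom Table 4 would let resume.

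**Conclusion.** The concern holds in a limited form. Read literally, 4.1.2 leaves out prior anti-PD-1 patients without autoimmune disease, and no other criterion expressly excludes one with a resolved event of the permanent-discontinuation type. Pneumonitis, recent or anticipated immunosuppression, inadequate laboratory values, antibody hypersensitivity, significant cardiovascular disease and the Appendix 5 diagnoses are already covered.

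This is an individual-safety point of minor to moderate severity. The ambiguity is plain from the text; how many patients it affects is unknown. It rests on two assumptions: that some sites apply the bullet literally, and that some screened patients have such a history.

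A reader might also infer that such patients were in fact enrolled, or that the primary incidence is distorted. Neither follows. The documents show only that the text permits entry, and Step 5 indicates that the effect on the overall estimate is probably small. SAP 3.5.7 already tabulates safety by prior anti-PD-1 therapy and in the OAK-LIKE population, which excludes these patients.

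**What to change.** 1. In 4.1.2 and the synopsis, add a stand-alone exclusion for all patients: a history, on prior anti-PD-1 therapy, of an immune-related event that meets the Appendix 9 criteria for permanent discontinuation, unless the patient has fully recovered and entry is approved in writing by the investigator (or delegate) and the Medical Monitor. The exception must be part of the criterion, because Protocol 9.2 does not allow eligibility waivers.
2. State that endocrine events stable on hormone or insulin replacement do not exclude, in line with Table 4. Say explicitly how Grade 4 hypophysitis is handled, since Table 4 discontinues it permanently.
3. State that the new criterion takes precedence over the anti-PD-1 carve-out in Inclusion Criterion 12, which can otherwise stay.
4. Leave the existing bullet unchanged for patients with autoimmune disease.

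The cost is one added criterion in two places and slightly fewer eligible prior anti-PD-1 patients. The change helps only patients not yet enrolled, and the documents do not give enrolment status.

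A medical-history flag for earlier anti-PD-1 immune events, with a matching split of the prior anti-PD-1 table in SAP 3.5.7, is optional. It would say little in a small group: 0 events in an illustrative 10 patients still leaves an upper 95% limit of 30.8%.
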